## 6.3 Dose modifications

### 6.3.1 Dose modification and dose delay

For patients who do not tolerate the protocol-specified dosing schedule, dose or schedule adjustments are permitted in order to allow the patient to continue the study treatment. The following guidelines need to be applied:

- If a patient experiences an AE meeting the criteria for DLT as outlined in [Section 6.2.4](#) (including events occurring after cycle 1 for Arm A and C or including events occurring after cycle 2 for Arm B), treatment should be withheld at the onset of the AE. Following resolution of the toxicity to grade 1 or to the patient's baseline value, the patient may resume study treatment after discussion with Novartis. If the investigator considers it to be in the patient's best interest to resume therapy before the toxicity has resolved to grade 1 or to the patient's baseline value, this may be permitted on a case by case basis after discussion with Novartis.
- For clinical management of suspected immune-related events, reference to consensus management guidelines is recommended such as those provided in the National Comprehensive Cancer Network (NCCN) Guidelines for the Management of Immunotherapy-Related Toxicities (available at : [https://www.nccn.org/professionals/physician\\_gls/default.aspx#immunotherapy](https://www.nccn.org/professionals/physician_gls/default.aspx#immunotherapy)), the American Society for Clinical Oncology clinical practice guideline for Management of Immune-Related Adverse Events in Patients Treated With Immune Checkpoint

Inhibitor Therapy ([Brahmer 2018](#)) or the European Society for Medical Oncology (ESMO) Clinical Practice Guidelines for Management of Toxicities from Immunotherapy ([Haanen 2017](#)). Note that in general, study treatment should be interrupted for grade 3 and 4 toxicities and for a subset of lower grade toxicities.

- Consider early referral to specialists with expertise in the diagnosis and management of immune-related AEs to thoroughly investigate events of uncertain etiology.
- Events not included in the study protocol or the reference guidance documents should be managed per institutional preference.

A scheduled dose (of either single-agent LAG525 or the combination of LAG525 and PDR001) may be delayed to recover from an unresolved AE. If a patient requires a dose interruption of > 21 days from the intended day of the scheduled dose due to an AE related to study drug(s), then the patient must be discontinued from the study, unless the patient is receiving clinical benefit and in the opinion of the investigator it is in the patient’s best interest to remain on study. The patient may restart treatment after discussion with Novartis.

Patients who discontinue the study for a study related AE or a study-related abnormal laboratory value must be followed as described in [Section 6.3.2](#).

[Table 6-5](#) outlines the recommended dose modifications for selected toxicities.

All interruptions or change to study drug administration must be recorded on the Dose Administration Record eCRF.

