**The following Grade 2 AEs related to study treatment are considered DLTs:**

Ocular disorders	Grade 2 eye pain or reduction of visual acuity are DLTs if they do not respond to topical therapy and do not improve to Grade 1 severity within 2 weeks of the initiation of topical therapy, OR if they require systemic treatment.
Pneumonitis	Grade 2 pneumonitis is a DLT if it does not resolve to $\leq$ Grade 1 within 7 days of starting corticosteroids.
Myocarditis	Grade 2 myocarditis is a DLT.
Colitis	Grade 2 colitis is a DLT if it persists $>$ 7 days despite treatment with corticosteroids.
Hepatic	Grade 2 ALT or AST accompanied by bilirubin $>1.5$ x ULN is a DLT.
Dermatologic	Grade 2 bullous disease that does not resolve to $\leq$ Grade 1 within 7 days of starting corticosteroids is a DLT.
Other adverse events	Other clinically significant toxicities, including a single event or multiple occurrences of the same event that lead to a dosing delay of $>$ 7 days within the DLT window, may be considered to be DLTs by the Investigators and Novartis, even if not CTCAE grade 3 or higher. Infusion reactions will not be considered as dose limiting because they are idiosyncratic and not related to dose.

\* Depending on the nature of the AE, there may be cases where immune-related Grade 2-3 AEs of any duration warrant declaration of a DLT and permanent study discontinuation (e.g. Stevens-Johnson Syndrome (SJS)). DLT determination not already outlined in this table will be made on a case-by-case basis after Investigator discussion with the Novartis Medical Monitor.

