Grade 3	Hold study treatment. Upon resolution to Grade $\leq$ 1 or baseline (hypertension, QTc) or $<$ 30 msec difference from baseline (QTc) within $\leq$ 7 days, may resume study treatment without dose modification after discussion with the Novartis Medical Monitor. Baseline ECG refers to the ECG(s) collected at screening.
Grade 4	Discontinue study treatment.
Other cardiovascular disorders	
Grade 2 (except myocarditis)	Hold study treatment. Upon resolution to Grade $\leq$ 1 or baseline, may resume study treatment without dose modification after discussion with the Novartis Medical Monitor.
Grade 2 myocarditis, or Grade $\geq$ 3 other cardiac disorders related to study treatment	Discontinue study treatment.
Gastrointestinal	
Diarrhea/colitis*	
Grade 1	May continue study treatment without dose modification. Manage per institutional standard guidelines which should include anti-diarrheal treatment, consideration of corticosteroid therapy, and hydration.
Grade 2	Hold study treatment. GI consultation. Upon resolution to $\leq$ Grade 1 and tapering of steroid requirement to $\leq$ 10 mg prednisone per day, resume study treatment without dose modification after discussion with the Novartis Medical Monitor.

Worst toxicity CTCAEa grade	Recommended Dose Modification
Grade 3	Hold study treatment. GI consultation. Upon resolution to ≤ Grade 1 and tapering of steroid requirement to ≤ 10 mg prednisone per day, consider resuming study treatment after discussion with the Novartis Medical Monitor.
Grade 4	Discontinue study treatment.
AST and/or ALT elevation	
Grade 2 AST and/or ALT	Hold study treatment. Manage per institutional practice. Upon resolution to ≤ Grade 1 or baseline, consider resuming study treatment without dose modification.
Grade 2 transaminitis with bilirubin >1.5 x ULN (unless Gilbert's syndrome)	Discontinue study treatment.
Grade 3 AST and/or ALT	Hold study treatment. Manage per institutional practices. Upon resolution to ≤ Grade 1 or baseline within 7 days, consider resuming study treatment without dose modification after discussion with the Novartis Medical Monitor. Otherwise, discontinue study treatment.
Grade 4 AST and/or ALT	Discontinue study treatment.
Isolated total bilirubin elevation**	
Grade 2	Hold study treatment. Upon resolution to ≤ Grade 1 or baseline, may continue study treatment without dose modification.

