Grade 4	Hold study treatment. Grade 4 treatment-related endocrinopathies, such as adrenal insufficiency, adrenocorticotrophic hormone (ACTH) deficiency, hyper- or hypothyroidism, or glucose intolerance, which resolve or are adequately controlled with physiologic hormone replacement (corticosteroids, thyroid hormones) or glucose-controlling agents, respectively, may not require discontinuation after discussion with and approval from the Novartis Medical Monitor.
Neurology	
Grade 1	Consider study treatment hold, particularly for clinical suspicion of Guillain-Barre syndrome, encephalitis, aseptic meningitis, transverse myelitis, or peripheral neuropathy.
Grade 2	Hold study treatment. In some cases, resuming study treatment may be considered after discussion with the Novartis Medical Monitor.
Grade 3 or Grade 4	Discontinue study treatment.
Dermatology (rash)	
Grade 1	Continue study treatment without dose modification. Topical steroids, antihistamines, topical emollients
Grade 2	Consider holding study treatment. Topical or oral steroids, antihistamines. If study treatment is held and resolution to ≤ Grade 1, resume study treatment without dose modification.
Grade 3 or Grade 4	Hold study treatment. Manage per institutional practice. After resolution to ≤ Grade 1, consider resuming study treatment after discussion with the Novartis Medical Monitor.

Worst toxicity CTCAEa grade	Recommended Dose Modification
Bullous dermatitis	Hold study treatment. Grade 1-2 bullous dermatitis: discussion with the Novartis Medical Monitor is required before considering resuming study treatment. Grade 3 bullous dermatitis: consider resuming therapy after expert consultation and documented discussion with the Novartis medical monitor. Grade 4 bullous dermatitis: discontinue study treatment
Stevens-Johnson syndrome (SJS), or Lyell syndrome/toxic epidermal necrolysis (TEN)	Permanently discontinue study treatment
Hematology	
Neutropenia (ANC)	
Grade 3 or Grade 4	Hold study treatment. Upon resolution to ≤ Grade 2 or baseline within ≤ 7 days, resume study treatment without dose modification, after discussion with the Novartis Medical Monitor.
Febrile neutropenia	
Grade 3 or Grade 4	Hold study treatment. Upon resolution of fever and improvement of neutropenia to ≤ Grade 2 or baseline, resume study treatment without dose modification, after discussion with the Novartis Medical Monitor.
Thrombocytopenia	

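### Section 6.3.1 allows resumption after any DLT-criteria event, Table 6-5 stops treatment for some of the same events, and the protocol does not say which governs

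*Protocol*

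**What the plan says.** Protocol Section 6.3.1 opens its list of bullets with "The following guidelines need to be applied". The first bullet begins "If a patient experiences an AE meeting the criteria for DLT as outlined in" Section 6.2.4, and adds that events after cycle 1 (Arms A and C) or after cycle 2 (Arm B) are included. Treatment is withheld at onset. After resolution to grade 1 or to the patient's baseline, "the patient may resume study treatment after discussion with Novartis". If the investigator judges earlier resumption to be in the patient's interest, "this may be permitted on a case by case basis after discussion with Novartis". The bullet names no exception and does not mention Table 6-5.

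Later in the same section, Table 6-5 is introduced as a table that "outlines the recommended dose modifications for selected toxicities". Many of its rows are imperatives to stop treatment. One row begins "Grade 2 myocarditis, or Grade" and ends in discontinuation. The row for SJS/TEN reads "Permanently discontinue study treatment".

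Table 6-4 supplies the DLT criteria on which the bullet relies. It says without further condition that "Grade 2 myocarditis is a DLT". It also makes Grade 2 ALT/AST with bilirubin above 1.5 x ULN a DLT, and every related Grade 3 or 4 event unless excepted. Its footnote allows that some immune-related events may warrant both a DLT and permanent discontinuation, with SJS as the example.

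**The concern.** For an event that is both a DLT under Table 6-4 and a stop row in Table 6-5, the protocol contains a permission to re-dose and an instruction not to. The permission sits in a list stated as binding; the instruction sits in a table called recommended. Nothing ranks them.

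For the patient, re-dosing after, say, myocarditis or combined transaminase and bilirubin elevation can be argued either way from the text. For the data, protocol Section 12 says that no authorized deviations are permitted, and SAP Section 2.4 tabulates a deviation category for patients who met withdrawal criteria but were not withdrawn. Whether re-dosing in these cases belongs in that category is undefined. Counts of adverse events leading to discontinuation (SAP Section 2.8.1.2) and duration of exposure (SAP Section 2.5.1.1) also depend on which text was followed.

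**Working it through.** No arithmetic beyond a count applies. The check takes each event, asks whether Table 6-4 makes it a DLT (so that the bullet applies), and reads the Table 6-5 action.

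| Event (related to treatment) | Table 6-4 | Section 6.3.1, first bullet | Table 6-5 |
|---|---|---|---|
| Grade 2 myocarditis | DLT, unconditional | May resume after discussion | Stop |
| Grade 2 ALT/AST with bilirubin >1.5 x ULN | DLT | May resume after discussion | Stop, unless Gilbert's syndrome |
| Grade 3 ALT/AST not back to grade 1 within 7 days | DLT (only resolution within 7 days, without significantly raised bilirubin, is excepted) | May resume after discussion | Stop if not resolved within 7 days |
| Grade 4 AST/ALT, pneumonitis, ocular, diarrhea/colitis, neurologic, pancreatitis, creatinine, platelets | DLT (no exception fits) | May resume after discussion | Stop |

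That gives 2 near word-for-word overlaps, 1 hepatic overlap in which the DLT condition and the stop condition largely coincide, and 8 kinds of Grade 4 event: 2 + 1 + 8 = 11 entries. This is a minimum; Grade 4 bullous dermatitis, for example, is a further one.

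Three readings that might dissolve the conflict:

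1. **Stopping in Table 6-5 might mean only a hold.** It does not. Where the table wants a route back it says so: the Grade 4 musculoskeletal row stops treatment but adds that resumption may be considered in some cases. The myocarditis and ALT/AST-with-bilirubin rows have no such addition.
2. **A precedence rule might exist elsewhere.** The general note under Table 6-5 says only that modifications follow the worst preceding toxicity. Neither the bullet nor the note refers to the other text.
3. **The status of each text might settle it.** The bullets are introduced as needing to be applied and the table as recommended, for selected toxicities. Taken literally, that favours the bullet over the more specific table. The wording therefore does not establish that the table overrides.

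Some rows do not belong in the overlap. Infusion reactions are not DLTs. Grade 3 thrombocytopenia without clinically significant bleeding is excepted. In general, a Grade 3 immune-related event that resolves to grade 1 or lower within 7 days of appropriate treatment is also not a DLT. Grade 3 pneumonitis, neurologic and similar rows therefore conflict only when Table 6-4 does not except the event. Several DLT-grade rows, such as Grade 3 diarrhea/colitis or Grade 3-4 rash, hold and then allow resumption, and fit the bullet.

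**The case against.** The strongest reply is that both texts can be obeyed. The bullet is permissive, so a site that stops treatment under Table 6-5 breaches nothing. A general default followed by a specific table is a normal structure, and many rows match the default. Both resumption sentences require discussion with the sponsor, so no site can re-dose under the bullet on its own authority.

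Most of this stands as a limit. It does not remove the point: the bullet authorises re-dosing that the stop rows rule out, and the discussion with the sponsor is given no rule to apply.

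A reader might infer four stronger things that the documents do not support.

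- **That sites following the protocol exactly would act in opposite ways.** Divergence is possible, but it would pass through the same sponsor, and resumption is never required.
- **That SJS/TEN is equally open.** The bullet lacks the exception, but the Table 6-4 footnote links SJS to permanent discontinuation, Table 6-5 does so for SJS and TEN, and the Amendment 09 rationale says that this was the purpose. The intended rule is not in doubt.
- **That every stop row conflicts.** The Table 6-4 exceptions above show otherwise.
- **That all Phase I and Phase II patients are covered.** The bullet has no phase limit and Section 4.1 places the Phase II groups under Arms A and B, but the Grade 3-4 criteria in Table 6-4 are headed as applying during dose escalation. Phase II coverage is an inference.

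**Conclusion.** The point holds as an internal inconsistency with no stated precedence. It is firmest for Grade 2 myocarditis and for Grade 2 ALT/AST with bilirubin above 1.5 x ULN (outside Gilbert's syndrome), and extends to unresolved Grade 3 ALT/AST and the listed Grade 4 events. It assumes that the bullet and the table each mean what they say, and that the absence of a linking sentence is not cured in a document outside the protocol and SAP.

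The number of patients affected cannot be derived from the documents. The Amendment 10 status section gives 39 active patients at 26 March 2019, 10 in escalation and 29 in expansion. The open question about Phase II scope therefore concerns 29 of 39 patients, about 74%.

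No effect on the primary endpoints is claimed. An event in the DLT window counts as a DLT whether or not the patient is later re-dosed, and the documents offer no basis for sizing an effect on ORR. What is affected is patient management, deviation classification, and the discontinuation and exposure summaries.

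**What to change.** Reconcile the first bullet of Section 6.3.1, the Table 6-4 footnote and Table 6-5. In Section 6.3.1, state:

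- which text governs when an event meets the DLT criteria and its Table 6-5 row says to stop treatment;
- whether either resumption sentence, including the one on resuming before resolution, applies to those rows;
- whether the bullet applies in Phase II.

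The choice of clinical rule is the sponsor's; this review takes no position on it. The cost is a sentence or two in an amendment or clarification letter. No new data or analysis is needed, although any re-dosing that has already followed such an event should be classified for deviations under whichever rule is confirmed.

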**Table 6-5 Recommended Dose Modifications for LAG525 and PDR001**

Worst toxicity CTCAE a grade	Recommended Dose Modification
Infusion reaction or hypersensitivity reaction	
Grade 1	Decrease infusion rate until recovery from the symptoms.
Grade 2	Stop infusion immediately, and keep line open. Follow institutional guidelines for the management and follow-up of infusion reaction. Restart infusion at 50% of previous rate under continuous observation. Ensure that there is a minimum observation period of 1 hour prior to restarting the infusion.
Grade 3 and Grade 4	If the AE recurs at the reinitiated slow rate of infusion, and despite oral pre-medication, then permanently discontinue study treatment. Discontinue infusion immediately, and discontinue study treatment. Provide supplemental oxygen, fluids, and other resuscitative measures as needed. Monitor vital signs (e.g. blood pressure, pulse, respiration, and temperature) every 15 ± 5 minutes until resolution.
Cytokine Release Syndrome (CRS)	
Grade 2	See instructions for Grade 2 Infusion Reaction above.
Grade 3 or Grade 4	Discontinue study treatment.  Follow-up CRS as per institutional guidelines. Take blood for cytokine measurements as specified in Section 8.4.1 – Laboratory evaluations.

Worst toxicity CTCAEa grade	Recommended Dose Modification
Ocular (uveitis, eye pain, blurred vision)	
Grade 1	Continue study treatment without dose modification. Ophthalmology consultation.
Grade 2	Hold study treatment. Urgent ophthalmology consultation. Upon resolution to $\leq$ Grade 1 may consider resuming study treatment without dose reduction after discussion with the Novartis Medical Monitor and in consultation with ophthalmology.
Grade 3 or Grade 4	Discontinue study treatment. Urgent ophthalmology consultation.
Pulmonary (pneumonitis)	
Grade 1	Consider study treatment hold. Manage per institutional practice. Consider resuming study treatment upon radiographic evidence of improvement.
Grade 2	Hold study treatment. Pulmonary and infection workup. Upon resolution to $\leq$ Grade 1, may resume study treatment without dose modification.
Grade 3 or Grade 4	Discontinue study treatment.
Cardiovascular	
ECG QTc-Interval prolonged; hypertension	
Grade 3	Hold study treatment. Upon resolution to Grade $\leq$ 1 or baseline (hypertension, QTc) or $<$ 30 msec difference from baseline (QTc) within $\leq$ 7 days, may resume study treatment without dose modification after discussion with the Novartis Medical Monitor. Baseline ECG refers to the ECG(s) collected at screening.
Grade 4	Discontinue study treatment.
Other cardiovascular disorders	
Grade 2 (except myocarditis)	Hold study treatment. Upon resolution to Grade $\leq$ 1 or baseline, may resume study treatment without dose modification after discussion with the Novartis Medical Monitor.
Grade 2 myocarditis, or Grade $\geq$ 3 other cardiac disorders related to study treatment	Discontinue study treatment.
Gastrointestinal	
Diarrhea/colitis*	
Grade 1	May continue study treatment without dose modification. Manage per institutional standard guidelines which should include anti-diarrheal treatment, consideration of corticosteroid therapy, and hydration.
Grade 2	Hold study treatment. GI consultation. Upon resolution to $\leq$ Grade 1 and tapering of steroid requirement to $\leq$ 10 mg prednisone per day, resume study treatment without dose modification after discussion with the Novartis Medical Monitor.

Worst toxicity CTCAEa grade	Recommended Dose Modification
Grade 3	Hold study treatment. GI consultation. Upon resolution to ≤ Grade 1 and tapering of steroid requirement to ≤ 10 mg prednisone per day, consider resuming study treatment after discussion with the Novartis Medical Monitor.
Grade 4	Discontinue study treatment.
AST and/or ALT elevation	
Grade 2 AST and/or ALT	Hold study treatment. Manage per institutional practice. Upon resolution to ≤ Grade 1 or baseline, consider resuming study treatment without dose modification.
Grade 2 transaminitis with bilirubin >1.5 x ULN (unless Gilbert's syndrome)	Discontinue study treatment.
Grade 3 AST and/or ALT	Hold study treatment. Manage per institutional practices. Upon resolution to ≤ Grade 1 or baseline within 7 days, consider resuming study treatment without dose modification after discussion with the Novartis Medical Monitor. Otherwise, discontinue study treatment.
Grade 4 AST and/or ALT	Discontinue study treatment.
Isolated total bilirubin elevation**	
Grade 2	Hold study treatment. Upon resolution to ≤ Grade 1 or baseline, may continue study treatment without dose modification.
Grade 3	Hold study treatment. Upon resolution to ≤ Grade 1 or baseline, may consider resuming study treatment after discussion with the Novartis Medical Monitor.
Grade 4	See footnote**. Otherwise, discontinue study treatment.
Asymptomatic amylase and/or lipase elevation***	
Grade 3 or Grade 4, not associated with symptoms or clinical manifestations of pancreatitis***	Continue study treatment. If levels do not resolve to ≤ Grade 2 within ≤ 14 days after the initial report, hold study treatment. Upon resolution to ≤ Grade 2, may resume study treatment without dose modification, after discussion with the Novartis Medical Monitor.
Pancreatitis	
Grade 2/radiologic evidence	Hold study treatment. Manage per institutional practice. Upon resolution to ≤ Grade 1, may resume study treatment without dose modification, if no clinical evidence of pancreatitis and after discussion with the Novartis Medical Monitor.
Grade 3 or Grade 4	Discontinue study treatment.
Renal	
Serum creatinine	
Grade 2	Hold study treatment. Manage per institutional practice. Upon resolution to ≤ Grade 1, may resume study treatment without dose modification after discussion with the Novartis Medical Monitor.
Grade 3 or 4	Discontinue study treatment.

Worst toxicity CTCAEa grade	Recommended Dose Modification
Musculoskeletal	
Grade 2 or Grade 3	Hold study treatment. Consider resuming study treatment without dose modification upon resolution to ≤ Grade 1 with appropriate management.
Grade 4	Discontinue study treatment. In some cases, resuming study treatment may be considered after discussion with the Novartis Medical Monitor and consultation with a rheumatologist.
Endocrine	
Hypothyroidism or hyperthyroidism	
Grade 2	May continue study treatment without dose modification. Management according to institutional practice.
Grade 3	Hold study treatment. Upon resolution to Grade ≤ 1 with appropriate management, may resume study treatment without dose modification.
Grade 4	May resume therapy following resolution or control with physiologic hormone replacement.
Other endocrine disorders	
Grade 2 and Grade 3	Hold study treatment. Upon resolution to Grade ≤ 1 with appropriate management, may resume study treatment without dose modification.
Grade 4	Hold study treatment. Grade 4 treatment-related endocrinopathies, such as adrenal insufficiency, adrenocorticotrophic hormone (ACTH) deficiency, hyper- or hypothyroidism, or glucose intolerance, which resolve or are adequately controlled with physiologic hormone replacement (corticosteroids, thyroid hormones) or glucose-controlling agents, respectively, may not require discontinuation after discussion with and approval from the Novartis Medical Monitor.
Neurology	
Grade 1	Consider study treatment hold, particularly for clinical suspicion of Guillain-Barre syndrome, encephalitis, aseptic meningitis, transverse myelitis, or peripheral neuropathy.
Grade 2	Hold study treatment. In some cases, resuming study treatment may be considered after discussion with the Novartis Medical Monitor.
Grade 3 or Grade 4	Discontinue study treatment.
Dermatology (rash)	
Grade 1	Continue study treatment without dose modification. Topical steroids, antihistamines, topical emollients
Grade 2	Consider holding study treatment. Topical or oral steroids, antihistamines. If study treatment is held and resolution to ≤ Grade 1, resume study treatment without dose modification.
Grade 3 or Grade 4	Hold study treatment. Manage per institutional practice. After resolution to ≤ Grade 1, consider resuming study treatment after discussion with the Novartis Medical Monitor.

Worst toxicity CTCAEa grade	Recommended Dose Modification
Bullous dermatitis	Hold study treatment. Grade 1-2 bullous dermatitis: discussion with the Novartis Medical Monitor is required before considering resuming study treatment. Grade 3 bullous dermatitis: consider resuming therapy after expert consultation and documented discussion with the Novartis medical monitor. Grade 4 bullous dermatitis: discontinue study treatment
Stevens-Johnson syndrome (SJS), or Lyell syndrome/toxic epidermal necrolysis (TEN)	Permanently discontinue study treatment
Hematology	
Neutropenia (ANC)	
Grade 3 or Grade 4	Hold study treatment. Upon resolution to ≤ Grade 2 or baseline within ≤ 7 days, resume study treatment without dose modification, after discussion with the Novartis Medical Monitor.
Febrile neutropenia	
Grade 3 or Grade 4	Hold study treatment. Upon resolution of fever and improvement of neutropenia to ≤ Grade 2 or baseline, resume study treatment without dose modification, after discussion with the Novartis Medical Monitor.
Thrombocytopenia	
Grade 3	Hold study treatment. Upon resolution to ≤ Grade 2 or baseline, resume study treatment without dose modification.
Grade 4	For Grade 3 associated with major bleeding, discontinue study treatment. Discontinue study treatment.
Anemia	
Grade 3 or Grade 4	Hold study treatment. Upon resolution to ≤ Grade 2 or baseline within ≤ 7 days, resume study treatment without dose modification.
Lymphopenia	
Any grade	Treatment-related lymphopenia does not require study treatment hold or discontinuation.
Other laboratory adverse events, not specified elsewhere in table and not included in the consensus guidelines	
Grade 3	Hold study treatment. Upon resolution to ≤ Grade 1, resume study treatment without dose modification.
Grade 4	Isolated Grade 4 electrolyte abnormalities not associated with clinical sequelae and corrected after appropriate management within 72 hours of their onset do not require discontinuation.  In the case of Grade 4 electrolyte imbalances associated with clinical sequelae, or not resolved to ≤ Grade 1 within 72 hours despite appropriate management, discontinue study treatment.

Worst toxicity CTCAE a grade	Recommended Dose Modification
Other non-laboratory adverse events, not specified elsewhere in table and not included in the consensus guidelines	
Grade 2	Consider study treatment hold, at Investigator discretion. Upon resolution to ≤ Grade 1, resume study treatment without dose modification.
Grade 3	Hold study treatment. Upon resolution to ≤ Grade 1, resuming study treatment must be discussed with the Novartis Medical Monitor.
Grade 4	Discontinue study treatment.

All dose modifications should be based on the worst preceding toxicity.

a Common Toxicity Criteria for Adverse Events (CTCAE)

\*Note: anti-diarrheal medication is recommended at the first sign of abdominal cramping, loose stools or overt diarrhea.

\*\*Note: If Grade 3 or 4 hyper-bilirubinemia is due to the indirect (non-conjugated) component only, and hemolysis as the etiology has been ruled out as per institutional guidelines (e.g., review of peripheral blood smear and haptoglobin determination), then delay study treatment until resolved ≤ Grade 1, and resume study treatment at the discretion of the investigator.

\*\*\*Note: A CT scan or other imaging study to assess the pancreas, liver, and gallbladder must be performed within one week of the first occurrence of any ≥ Grade 3 of amylase and/or lipase.

